10.3.4 Safety Variables

Safety assessments will include the evaluation of AEs, including local tolerability (stinging/burning, pruritus, and erythema), clinical laboratory assessments, vital signs, 12-lead ECGs, and physical examinations.

10.3.4.1 Clinical Laboratory Safety Assessments

10.3.4.1.1 Clinical Laboratory Tests to be Performed

Samples for the following laboratory tests will be collected at the time points specified in the Schedule of Events (Section 2.2).

Hematology:	hemoglobin, hematocrit, red blood cell (RBC) count, RBC indices, mean corpuscular hemoglobin, mean corpuscular hemoglobin concentration, platelet count (or estimate), white blood cell count including differential
Serum Chemistry:	albumin, total bilirubin, total protein, calcium, alkaline phosphatase, alanine aminotransferase, aspartate aminotransferase, blood urea nitrogen, creatinine, glucose, sodium, potassium, chloride, bicarbonate, lactate dehydrogenase, uric acid, total cholesterol, high-density lipoprotein, low-density lipoprotein, triglycerides
Coagulation Panel:	prothrombin time, partial thromboplastin time, fibrinogen
Urinalysis:	pH, specific gravity, blood, glucose, protein, ketones
Pregnancy Test:	for women of childbearing potential only; serum at Screening, urine at each other visit.
Serology	Hepatitis B surface antigen, and hepatitis C

All blood samples for the clinical laboratory tests must be taken in a fasting state, at least 8 hours after the previous drug application.

Blood and urine samples for hematology, and serum chemistry will be sent to a central laboratory for analysis. Urine pregnancy tests and dipstick will be conducted at the study sites.

10.3.4.1.2 Specimen Handling Requirements

The transmission of infectious agents may occur through contact with contaminated needles and blood or blood products. Consequently, appropriate blood and body fluid precautions should be employed by all study personnel involved in the collection of blood and handling of specimens in

both the clinic and laboratory settings. Refer to current recommendations of the appropriate authorities.

In addition to appropriate handling of subject samples, specific regulations exist regarding the shipment of biologic/etiologic samples. Procedures and regulations for the packaging and shipping of infectious samples are outlined in the study laboratory manual. The investigator is responsible for ensuring that all study samples that are to be transported to another location are packed and shipped appropriately according to the applicable regulations.

Samples for assessment of clinical laboratory tests will be transported to the Clinical Reference Laboratory (see the study laboratory manual for addresses).

10.3.4.1.3 Evaluation of Clinical Laboratory Values

The normal ranges of values for the clinical laboratory assessments in this study will be provided by the responsible laboratory and submitted to Mayne Pharma LLC prior to beginning the study. They will be regarded as the reference ranges on which decisions will be made.

If a laboratory value is out of the reference range, it is not necessarily clinically significant. The investigator must evaluate the out-of-range values and record his or her assessment of the clinical significance in the appropriate eCRF.

All clinical laboratory values that in the investigator's opinion show clinically significant or pathological changes during or after termination of treatment must be reported as AEs and followed, as described in Section [11.2.5](#).

All measurements described in this section are recognized standard methods.

10.3.4.2 Clinical Examinations

10.3.4.2.1 Vital Signs

Vital signs, including height and weight (only assessed at Screening), blood pressure, and pulse will be measured.

10.3.4.2.2 Twelve-lead Electrocardiogram

A standard 12-lead ECG will be performed after the subject has been supine for at least 5 minutes. All ECG recordings will be identified with the subject number, date, and time of the recording. Gel ECG electrodes may be used for ECGs because they are more conductive and cause less trauma on compromised skin. Efficacy assessments should be conducted before ECGs to avoid possible artefact/changes from the ECG.

For subjects in the PK substudy, additional ECGs will be performed postdose during serial blood sampling on Day 1 and Day 30.

If there is a marked prolongation of the QT/QTc interval during treatment, a subject should be discontinued from the IP but remain in the study until full resolution of the event. The DSMB will be informed immediately of such an occurrence.

10.3.4.2.3 Physical Examination

A complete physical examination excluding the genitourinary examination will be performed at Screening, while limited physical examinations (to include HEENT, cardiorespiratory, abdomen, and range of motion) will be performed as indicated in the Schedule of Events (Section [2.2](#)).

10.3.4.2.4 Other Safety Variables

Local tolerability will be assessed on a 0-3 scale (none, mild, moderate, severe). All application site reactions will be recorded as TEAEs in the diary. These should include the date and severity of the TEAE.

10.3.4.3 Adverse Events

The definitions and management of AEs, and any special considerations for AEs, are provided in Section [11](#).

11. ADVERSE EVENTS

11.1. Definitions

11.1.1 Adverse Events

An AE is defined as any untoward medical occurrence in a patient or clinical investigation subject administered a pharmaceutical product that does not necessarily have a causal relationship with this treatment. An AE can therefore be any unfavorable and unintended sign (including an abnormal laboratory finding, for example), symptom, or disease temporally associated with the use of a medicinal product, whether or not related to the medicinal product.

Pre-existing diseases or conditions will not be considered AEs unless there is an increase in the frequency or severity, or a change in the quality, of the disease or condition. (Worsening of a pre-existing condition is considered an AE.)

Events that occur in subjects treated with control product are also considered AEs.

11.1.2 Adverse Drug Reaction

All noxious and unintended responses to an investigational product related to any dose should be considered adverse drug reactions (ADRs).

The phrase “responses to an investigational product” means that a causal relationship between an investigational product and an AE is at least a reasonable possibility, i.e., the relationship cannot be ruled out. All AEs judged by either the reporting investigator or the sponsor as having a reasonable causal relationship to an IP qualify as ADRs.

All AEs for which the judgment of relationship to IP is “possible” or higher will be considered ADRs. If a relationship to IP is not provided, then the AE must be treated as if it were “possible.”

11.1.3 Unexpected Adverse Event/Adverse Drug Reaction

An expected AE or ADR is one for which the nature or severity is consistent with the known AE profile of the product. For a preapproval test product, the known information is contained in the IB. For a marketed product, the known information is contained in the current package insert for the product.

An unexpected adverse event (UAE) or unexpected adverse drug reaction (UADR) is one for which the nature or severity of which is not consistent with the applicable product information (e.g., IB for an unapproved investigational product or package insert/summary of product characteristics for an approved product). For example, hepatic necrosis would be unexpected (greater severity) if the IB only listed elevated hepatic enzymes or hepatitis. Likewise, cerebral thromboembolism and cerebral vasculitis would be unexpected (greater specificity) if the IB only listed cerebral vascular accidents.

Furthermore, reports that add significant information on specificity or severity of a known, already documented adverse reaction constitute unexpected events.

11.1.4 Serious Adverse Events/Drug Reaction

A serious adverse event (SAE) is any untoward medical occurrence that at any dose:

- results in death
- is life-threatening
NOTE: The term “life-threatening” in the definition of “serious” refers to an event in which the subject was at risk of death at the time of the event; it does not refer to an event that hypothetically might have caused death if it were more severe.
- requires inpatient hospitalization or prolongation of existing hospitalization
NOTE: Inpatient hospitalization is defined as 24 hours in a hospital or an overnight stay. An elective hospital admission to treat a condition present before exposure to the IP, or a hospital admission for a diagnostic evaluation of an AE, does not qualify the condition or event as an SAE. Further, an overnight stay in the hospital that is only due to transportation, organization, or accommodation problems and without medical background does not need to be considered an SAE.
- results in persistent or significant disability/incapacity
- is a congenital anomaly
NOTE: A congenital anomaly in an infant born to a mother who was exposed to the IP during pregnancy is an SAE. However, a newly diagnosed pregnancy in a subject that has received an IP is not considered an SAE unless it is suspected that the IP(s) interacted with a contraceptive method and led to the pregnancy.
- is an important medical event
NOTE: Medical and scientific judgment should be exercised in deciding whether it is appropriate to consider other situations serious, such as important medical events that may not be immediately life-threatening or result in death or hospitalization but may jeopardize the subject or may require intervention to prevent one of the other outcomes listed in the definition above. Examples of such events are intensive treatment in an emergency room or at home for allergic bronchospasm, blood dyscrasias, or convulsions that do not result in hospitalization, development of drug dependency, or drug abuse. The occurrence of malignant tumors is also to be considered serious.

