11.2. Event Assessment and Follow-up of Adverse Events

The occurrence of an AE or SAE may come to the attention of study personnel during study visits and interviews of a study participant presenting for medical care or upon review by a study monitor.

All reported AEs, including local and systemic AEs not meeting the criteria for SAEs, will be captured on the appropriate eCRF. Information to be collected includes event description, time of onset, clinician's assessment of severity, relationship to study product (assessed only by those with the training and authority to make a diagnosis), and time of resolution/stabilization of the event. All reported AEs occurring while on study must be documented appropriately regardless of relationship. All reported AEs will be followed to adequate resolution.

Any medical condition that is present at the time that the participant is screened will be considered as baseline and not reported as an AE. However, if the study participant's condition deteriorates at any time during the study, it will be recorded as an AE.

Changes in the severity of a reported AE will be documented to allow an assessment of the duration of the event at each level of severity to be performed. AEs characterized as intermittent require documentation of onset and duration of each episode.

Study clinic personnel will record all reportable events with start dates occurring any time after informed consent is obtained until 14 (for nonserious AEs) or 30 days (for SAEs) after the last day of study participation. At each study visit, the investigator will inquire about the occurrence of AE/SAEs since the last visit. Events will be followed for outcome information until resolution or stabilization.

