11.2.6.3 Nonserious Adverse Events

Nonserious AEs will be recorded in the eCRF and reported by Premier Research to Mayne Pharma LLC in aggregate monthly status reports.

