11.3.2 Pregnancy

All WOCBP who participate in the study should be counseled on the need to practice highly effective birth control and on the importance of avoiding pregnancy during study participation. Women should be instructed to contact the investigator or study staff immediately if pregnancy occurs or is suspected.

Pregnancy testing will be conducted prior to administration of the IP on every woman of childbearing potential. A woman who is found to be pregnant at the Screening Visit will be excluded from the study and considered to be a screening failure.

A woman who becomes pregnant during IP treatment will be immediately discontinued from study treatment. The investigator must report the pregnancy of any woman who becomes pregnant during or within 30 days after discontinuing treatment as if it were an SAE within 24 hours of learning of the pregnancy, to Premier Research Pharmacovigilance using the Pregnancy Data Collection Form via the same fax number and/or email address as for SAE reporting. The

investigator should contact the designated individual(s) who receive SAE notification and record information related to the pregnancy on an SAE and AE form (entering the event temporarily as nonserious on both forms) provided by the sponsor or its designee. If a partner of a male study subject becomes pregnant, the investigator must report the pregnancy as soon as possible after learning of it to the Premier Research Pharmacovigilance using the Pregnancy Data Collection Form. A separate pregnant partner ICF will be required.

Early Termination Visit assessments are required as soon as possible after learning of the pregnancy in a study subject. The investigator is also responsible for following the pregnancy until delivery or termination. These findings must be reported on the Exposure in Utero form and forwarded to the designated individual(s). The event meets the SAE criterion only if it results in a spontaneous abortion or a congenital anomaly.

Among the clinical studies, 12 pregnancies were reported: 4 resulted in normal births; 5 resulted in spontaneous abortions (none of which was considered related to CD5789); 1 was electively aborted, and 2 were lost to follow-up (IB for CD5789 Cutaneous Formulation).

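### The SAE definition in 11.1.4 exempts inpatient admissions made to work up an AE, and 11.3.2 contradicts 11.1.4 on when a pregnancy is serious

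*Protocol*

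**What the plan says.** Section numbers refer to the Amendment 2 text, the latest version of Section 11 that is shown.

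**Hospitalization.** Section 11.1.4 lists as serious an event that "requires inpatient hospitalization or prolongation of existing hospitalization". The note beneath says "Inpatient hospitalization is defined as 24 hours in a hospital or an overnight stay". It then takes three kinds of stay out of the criterion: elective admission for a condition that predates exposure, admission to investigate an AE, and overnight stays for purely logistical reasons. The second is worded "or a hospital admission for a diagnostic evaluation of an AE, does not qualify the condition or event as an SAE". A separate important-medical-event criterion adds "Medical and scientific judgment should be exercised in deciding whether it is appropriate to consider other situations serious".

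**Pregnancy.** The congenital-anomaly note in 11.1.4 says that a newly diagnosed pregnancy "is not considered an SAE unless it is suspected that the IP(s) interacted with a contraceptive method and led to the pregnancy". Section 11.3.2 says "The event meets the SAE criterion only if it results in a spontaneous abortion or a congenital anomaly".

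**What follows from the label.** SAEs go to the contract research organisation within 24 hours (11.2.6.1), and suspected serious drug reactions go to the sponsor immediately (11.2.6.2). For the rest, 11.2.6.3 says "Nonserious AEs will be recorded in the eCRF and reported by Premier Research to Mayne Pharma LLC in aggregate monthly status reports". Section 13.1.6.2 summarizes SAEs separately.

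**The concern.** Two of the three exceptions concern stays in which nothing new has happened to the subject: planned care of an old condition, or a bed needed for travel reasons. The diagnostic exception differs in kind. As worded it covers an AE that arose on study drug and was worrying enough to admit the subject, with no limit on length of stay, cause or relationship to treatment.

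The protocol has reason to watch for such events. It says that absorption in lamellar ichthyosis may exceed that in healthy volunteers (5.2). It stops treatment for clinically significant liver-test or lipid changes (9.4.1), and it singles out QT prolongation (10.3.4.2.2). Safety against vehicle is part of the primary objective (6.1).

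Pregnancy matters for a similar reason. Section 5.3 reports reproductive toxicity in animals and a possibly lower safety margin at higher concentrations and larger treated areas. Sites given two rules for when a pregnancy is serious may code the same event differently.

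**Working it through.** No figure in the plan has to be reproduced, so the check sets the clauses side by side.

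**1. A diagnostic admission.** Take a new AE on study drug, with an overnight stay only to find its cause.
- Criterion plus definition (11.1.4): the stay is overnight, so the event counts as hospitalized and serious.
- Note (11.1.4): the purpose of the stay is evaluation of an AE, so the stay does not make the event serious.
- Other criteria: the event is serious only if it is fatal, life-threatening or disabling, or if the investigator judges it an important medical event.
- If none applies, it is nonserious. No 24-hour report under 11.2.6.1 is due, the immediate report of serious reactions under 11.2.6.2 is not triggered, it does not enter the separate SAE summary, and it reaches the sponsor in the monthly aggregate.

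**2. A pregnancy in a subject.**

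| Situation | 11.1.4 | 11.3.2 |
|---|---|---|
| Congenital anomaly | Serious | Serious |
| Spontaneous abortion | Serious if a general criterion is met | Serious |
| Suspected interaction of study drug with contraceptive | Serious | Not serious on that ground |
| Fatal, life-threatening or needing admission, e.g. ectopic pregnancy with an inpatient stay | Serious | Not serious, if the sentence covers complications |
| Uncomplicated normal birth | Not serious | Not serious |

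The third row is a direct contradiction. The fourth is one on the plain reading of the sentence in 11.3.2, because the general criteria in 11.1.4 contain no exception for pregnancy.

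**3. Timing for pregnancies.** Section 11.3.2 requires a pregnancy during treatment, or within 30 days after it, to be reported like an SAE within 24 hours, with the event provisionally entered as nonserious. The investigator follows it to its end and reports the outcome on a dedicated form, for which no deadline is given. The monthly route in 11.2.6.3 therefore does not govern the first report of a subject's pregnancy.

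**4. Scale.** 120 subjects randomized 1:1:1 give 120/3 = 40 per arm. One subject whose only SAE is relabelled moves that arm's SAE percentage by 1/40 = 2.5 points. How many would be relabelled cannot be worked out: the protocol gives no SAE rate, no admission rate, and no share of admissions that are diagnostic.

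**The case against.** The strongest reply is that the note is part of the definition, so a diagnostic admission never met the hospitalization criterion, and that the remaining criteria still catch anything grave. Other safeguards exist too. Marked QT prolongation goes to the DSMB at once (10.3.4.2.2), clinically significant laboratory changes must be recorded as AEs (10.3.4.1.3), and all AEs are tabulated, with separate summaries by severity and relationship (13.1.6.2). Such events are relabelled, not lost.

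Much of this stands. It means that an undercount is possible, not certain. It does not remove the problem: the important-medical-event route depends on one investigator's judgement exercised against an explicit exclusion, and the label decides both expedited reporting and entry in the SAE table.

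On pregnancy, the sentence in 11.3.2 can be read as speaking of the pregnancy alone, which leaves a complication to be reported as its own AE. That reading removes the fourth row of the table but not the third, since the note in 11.1.4 also speaks of the pregnancy itself.

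Four stronger readings are tempting, and the documents do not support them.
- *Serious pregnancy events wait for the monthly report.* Section 11.3.2 requires a 24-hour report of a subject's pregnancy whatever its class.
- *Every other pregnancy outcome is wrongly excluded.* An uncomplicated normal birth meets no SAE criterion.
- *On-treatment events are lost through a shorter collection window.* The period runs "until 14 (for nonserious AEs) or 30 days (for SAEs) after the last day of study participation", so it does not bear on events during treatment.
- *The undercount can be quantified*, for example as a higher chance of seeing no SAE in the 80 actively treated subjects. That needs a diagnostic share of admissions that appears nowhere in the protocol, and the answer would only restate the assumption.

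The 24-hour and monthly rules also describe different steps, investigator to contract research organisation and contract research organisation to sponsor, so they are not two values of one delay.

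**Conclusion.** The point holds as a defect in wording with practical consequences. Applied as written, the note in 11.1.4 lets an on-treatment AE with an inpatient diagnostic stay be handled as nonserious when no other criterion or judgement makes it serious. Section 11.3.2 and Section 11.1.4 cannot both be applied to a pregnancy with suspected contraceptive interaction and, on the plain reading, conflict on pregnancy complications that meet a general criterion. The pregnancy part is a conflict of classification only.

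The size of any undercount is unknown. The 2.5 points per relabelled subject shows how coarse the SAE percentages are and is not an estimate of bias.

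The conclusion rests on the Amendment 2 text of Section 11. A later amendment is shown only in part, without its Section 11. The same two clauses stand in both versions of Section 11 that are shown, so they probably persist, but this should be confirmed. SAE definitions and reporting duties are fixed in the protocol and are not matters left to the SAP.

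**What to change.** - **11.1.4, hospitalization note:** delete the part of the quoted exception before its comma, so that admission for diagnostic evaluation of an AE is no longer exempt. Keep the exceptions for elective admission for a condition present before exposure and for stays due to transport, organization or accommodation.
- **11.3.2:** replace the restrictive sentence with a statement that a pregnancy complication or outcome is an SAE if it meets any criterion in 11.1.4, and that spontaneous abortion, congenital anomaly and a suspected interaction of study drug with a contraceptive also count.
- **Consistency:** make the contraceptive-interaction note in 11.1.4 and the revised 11.3.2 say the same thing, and carry the change into the SAE form guidance.

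The cost is protocol and form wording, plus a few more SAE reports, some of which will prove benign. No dose, visit or analysis changes.

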11.1.5 Significant Adverse Events

Other significant AEs are defined as marked hematological and other laboratory abnormalities (other than those meeting the definition of serious) and any events that led to an intervention, including withdrawal of test drug, dose reduction, or significant additional concomitant therapy.

11.1.6 Treatment-Emergent Adverse Events

An AE is defined as treatment emergent if the first onset or worsening is after the first application of IP (trifarotene or vehicle) and not more than 14 days after the last application of IP.

